8.2 Data Collection Forms

The data collection process consists of direct data entry at the study sites into the EDC system(s) provided by the DSC. This process excludes the SUC which will be captured on a calendar prior to entry. The DSC will provide the sites with a final set of guided source documents and instructions. The guided source documents will be distributed electronically to the participating CTPs. These documents are used to collect data in the event the database is unavailable. Data entry of the eCRFs should be completed according to the instructions provided and project specific training. The investigator is responsible for maintaining accurate, complete and up-to-date records, and for ensuring the completion of the eCRFs for each research participant. The DSC is not responsible for maintaining any source documentation related to the study, including any films, tracings, computer discs or tapes.

8.3 Data Acquisition and Entry

Data entry into electronic CRFs shall be performed by authorized individuals. Selected eCRFs may also require the investigator's written signature or electronic signature, as appropriate. Electronic CRFs will be monitored for completeness, accuracy, and attention to detail during the study.

8.4 Site Responsibilities

The data management responsibilities of each individual CTP will be specified by the DSC.

8.5 Data Center Responsibilities

The DSC will 1) develop a data management plan and will conduct data management activities, 2) provide final eCRFs for the collection of all data required by the study, 3) develop data dictionaries for each eCRF that will comprehensively define each data element, 4) conduct ongoing data monitoring activities on study data from all participating CTPs, 5) monitor any preliminary analysis data clean up activities, and 6) rigorously monitor final study data clean up.

8.6 Data Editing

Completed data will be entered into the DSC automated data acquisition and management system. If incomplete or inaccurate data are found, a data clarification request will be generated and distributed to sites for a response. Sites will resolve data inconsistencies and errors and enter all corrections and changes into the DSC automated data acquisition and management system.

8.7 Data Transfer

Data will be transmitted by the DSC to the NIDA central data repository as requested by NIDA. The DSC will conduct final data quality assurance checks and "lock" the study database from further modification. The final analysis dataset will be returned to NIDA, as requested, for storage and archive.

8.8 Training

The training plan for CTP staff includes provisions for training on assessments, eCRF completion guidelines, data management procedures, and the use of computerized systems.

8.9 Data QA

To address the issue of data entry quality, a random sample of eCRFs will be selected from each CTP for a source-to-database audit according to the DSC's Internal Audit SOP. The random selection process should occur as a regular part of the data management process, but the frequency of sampling can remain flexible during data capture. The results of the audits should be made available to the study executive group at any time during the study, and a final summary report will be required as part of the pre-lock procedures. An acceptable quality level will be established as a part of the data management plan.

9.0 COUNSELOR SELECTION, TRAINING, AND SUPERVISION

9.1 Introduction:

This study will utilize a centralized training of counselors and a training-of-trainers/supervisors model.

9.2 Counselor/Supervisor Selection

Study counselors and supervisors will be chosen from the participating CTPs. The educational background, credentials, and experience of the clinical staff implementing the intervention will vary between CTPs. All counselors and supervisors will be assessed during the recruitment process on their 12-step knowledge and familiarity with using a 12-step model during treatment. Potential counselors for the study will be identified by the Site PI in conjunction with CTP supervisors. After informed consent process and successfully completing a screening session, a select number of counselors will be chosen randomly from the available pool to serve as STAGE-12 counselors, and participate in a national training program. All training sessions conducted by trainees for selection and certification will be recorded. At least one counselor and one supervisor from each participating CTP will attend this training.

9.3 STAGE-12 Counselor Training

The STAGE-12 training will be completed prior to study initiation. Counselors will be briefed about the general study aim of the merits of 12-step facilitation in substance abuse settings. Counselors hired after training will be trained at their local site with consultation from the Lead Node training group.

Appropriate training for the STAGE-12 intervention requires completion of a didactic seminar and supervised training cases, as required. The STAGE-12 training will include a didactic seminar, presented in a face-to-face training by experts in TSF and Intensive Referral. The training seminar will include a review of basic 12-step principles, topic-by-topic review of the STAGE-12 manual, several role play and practice exercises, discussion of case examples, and rehearsing strategies for difficult or challenging cases.

9.4 Certification and Additional Training for Supervisors

In addition to the therapy training, treatment supervisors will attend an extra training session. This component will focus on providing supervision and using the adherence scales to rate recorded sessions. Those ratings will be compared to ratings made by a Lead Node expert trainer in the study intervention.

Ongoing Supervision of Counselor: During the study, STAGE-12 counselors will receive regularly scheduled individual supervision that will include review and discussion of randomly selected, recorded sessions. Supervisors will rate the sessions for adherence prior to the individual meeting with the counselor.

Ongoing Supervision of Supervisors: In order to ensure ongoing supervisor competency, supervisors will have conference calls with experts in the intervention to answer questions that arise about the treatment and supervision. Supervisors will also submit adherence ratings for expert review. The Lead Node will co-rate 20% of the sessions to assure supervisor fidelity.

10.0 STATISTICAL ANALYTIC PLAN

10.1 Objectives of the analysis

The primary objective of this study is to examine the degree to which 12-Step Facilitation Therapy (STAGE-12) integrated into treatment as usual (TAU) reduces days of stimulant use compared to TAU alone.

10.2 Randomization

Participants will be randomized to one of the two treatment conditions. Randomization will be stratified by site and by whether the participant was court-mandated for treatment vs. not court-mandated. The randomization process will be conducted in a centralized process through the Data and Statistical Center (DSC).

10.3 Primary Outcomes

10.3.1 Hierarchical linear model

The primary outcome variable will be percent of days of stimulant use over the assessment window, based on Substance Use Calendar alone and assessed at baseline, weeks 4 and 8/end of treatment, 3 months and 6 months. This measure will be analyzed using hierarchical linear models. Specifically, the trajectory over time for an individual patient will be described by the Level-1 model

(1)
$$Y_{ijk} = X_i \varphi + \beta_{0ij} + \beta_{ij} t_{ik} + \varepsilon_{ijk}, \qquad k=1,..., n_i$$

where Y_{ijk} and ε_{ijk} are percent of days of stimulant use and error term of participant i at site j at post-baseline assessment k, β_{0ij} is the baseline percent of stimulant use, β_{ij} is the slope for participant i, t_{ik} is the number of weeks at post-baseline assessment k, n_i is the number of post-baseline assessments for participant i, which can differ between the participants reflecting attrition; X_i is a baseline variable describing whether participant i was court mandated for treatment ($X_i = 1$) vs. not court-mandated for treatment ($X_i = 0$).

The Level-2 model describes the slope for participant *i* as a function of the treatment arm:

(2)
$$\beta_{ii} = \alpha_{0i} + \alpha_1 I(STAGE-12) + b_{ii}$$

Here α_{0j} is the intercept for participants at the *j*th treatment site, α_1 is the effect of the STAGE-12 treatment, *I*(STAGE-12) is a 0-1 STAGE-12 treatment indicator and b_{ij} is a subject-specific random error term.

The Level-2 model also describes the baseline outcome measure for participant i:

$$\beta_{0ij} = \alpha_{00j} + b_{0ij}$$

Here α_{00j} is the intercept for participants at the *j*th treatment site and b_{0ij} is a subject-specific random error term.

The assumptions of the model are: a) $\mathbf{e}_{ij} = (\varepsilon_{ij1},...,\varepsilon_{ijn_i})^T$ are independent $N(0,\Sigma_i)$ where Σ_i depends in i only through its dimension, b) b_{ij} are independent $N(0, \sigma_b^2)$, uncorrelated with ε_{ijk} , c) b_{0ij} are independent $N(0, \sigma_0^2)$, uncorrelated with b_{ii} and ε_{ijk}

The primary analysis will evaluate the hypotheses H_0 : $\alpha_1 = 0$ vs. H_1 : $\alpha_1 \neq 0$ and rejection of the null hypothesis with $\alpha_1 < 0$ would indicate that STAGE-12 treatment reduces percent of days of substance use compared to TAU.

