10.6 Sample Size and Power Calculations

[figure not shown]
The sample size required for detecting a time by group interaction is estimated using the formulas due to Hedeker et al. (Hedeker, Gibbons, Waternaux, 1999). The following assumptions are employed. Four replicate, continuous, approximately normally distributed outcome (Percent of Days of Drug Use) measurements are to be obtained at 4, 8, 13 and 26 weeks (the baseline value is to be entered as a covariate). A two-sided type-I error rate (alpha) is set at 0.05 and power (1-beta) is assumed as 80%.

The expected effect size was determined by incorporating information from two sources. First, in the Brown, Serganian, et al. (2002) study of group-based TSF versus an active comparison therapy (relapse prevention [RP]), the standard deviation for "days of use in previous 90 days" was 24 days in the TSF group and 17.7 days in the RP group, giving a pooled estimate of the standard deviation of 21.3 days, or 23.7% of days of substance use over the 6-month assessment window. Second, clinicians and program directors from multiple CTPs in the CTN were asked about what they viewed as a potentially clinically meaningful difference between their TAU and an experimental treatment such as TSF. They indicated that a 10% difference, on average, in percent days of use between TAU and a new therapy would be clinically meaningful. A 10% difference divided by a standard deviation of 23.7% gives a standardized effect size of 10/23.7 = 0.42. Effects of this magnitude are in the 'small' to 'medium' range in the power analysis literature (Cohen, 1983). Based on or anticipated ability to track, follow, and assess participants at the follow-up points, a total retention rate of 70% for the duration of the trial was assumed, with the dropout rate occurring evenly over the 4 post baseline points is assumed; however, it should be noted that the follow-up rates in the Brown, Serganian, et al. (2002) was only about 50% at the 6-month follow-up. Compound symmetry with a correlation parameter of 0.5 is also assumed; however, there is no information available on the correlation pattern between observations.

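### Court mandate, a randomisation stratum, is adjusted for in level but not in the slope equation where the primary treatment effect is tested; a minor efficiency loss that one extra term removes

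*Protocol*

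**What the plan says.** Section 10.2 of the protocol: "Randomization will be stratified by site and by whether the participant was court-mandated for treatment vs. not court-mandated".

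Section 10.3.1 then prints the primary model term by term. In cleaned-up notation:

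- Level 1: Y_ijk = X_i*phi + beta_0ij + beta_ij*t_ik + error, where X_i "is a baseline variable describing whether participant i was court mandated for treatment" (1 = mandated, 0 = not).
- Level 2, slope, described "as a function of the treatment arm": beta_ij = alpha_0j + alpha_1*I(STAGE-12) + b_ij.
- Level 2, baseline level: beta_0ij = alpha_00j + b_0ij.

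"The primary analysis will evaluate the hypotheses" alpha_1 = 0 against alpha_1 not equal to 0. So alpha_1 is the effect of STAGE-12 on the slope, and equation (2) is the only place where treatment appears.

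Sections 10.4.1.1.1, 10.4.1.1.3 and 10.4.2.1.1 to 10.4.2.1.4 build their hierarchical models on the pattern of the primary one.

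**The concern.** Both factors are randomisation strata, but they are treated differently. Site has its own level (alpha_00j) and its own slope (alpha_0j). Court mandate has only a level (phi). The protocol gives no reason for the difference and adds no mandate-by-time term elsewhere. Because the equations are printed in full, an analyst who follows them would fit no such term.

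If mandated clients improve faster or slower than voluntary ones, much of that difference is left in the between-person slope variance, although stratification has balanced it across arms and the model could remove it. Precision on the tested coefficient is then given away. A second possible consequence concerns dropout. If retention depends on mandate and arm together, likelihood estimation relies on the relation between mandate and trajectory being in the model. The protocol plans on 30% attrition and considers 50% (section 10.6).

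**Working it through.** The plan states no figure on this point, so there is none to reproduce. The structural reading comes first, then its size.

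**Structure**

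| Term | Level | Slope |
|---|---|---|
| Site | alpha_00j | alpha_0j |
| Court mandate | X_i*phi | none |
| STAGE-12 | none | alpha_1 (tested) |

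**Inputs from section 10.6.** Visits at weeks 4, 8, 13 and 26; SD 23.7; compound symmetry with rho 0.5; 30% attrition; about 200 per arm. For the test, "A two-sided type-I error rate (alpha) is set at 0.05 and power (1-beta) is assumed as 80"%.

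**Inputs assumed, because the documents do not give them.** Mandate prevalence 30 to 50%; difference in trajectory between mandate groups of 0, 10, 15 or 20 points at week 26; random-slope SD between 0 and 0.5 per week; the dropout patterns described below. All variances are treated as known.

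**Step 1: what is left in the slope.** A 10-point divergence at week 26 is 10/26 = 0.385 points per week. With prevalence p, the omitted term adds slope variance of 0.385^2 * p(1-p). At p = 0.5 this is 0.148 * 0.25 = 0.037, an SD of 0.19 per week.

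Not all of the divergence is left there, because phi picks up part of it. With complete data and rho 0.5, the inverse correlation matrix is 2(I - 0.2J). Then 1'W1 = 1.6, 1'Wt = 20.4 and t'Wt = 809.6. The share absorbed by the level term is 20.4^2 / (1.6 * 809.6) = 416.2 / 1295.4, about 32%.

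**Step 2: standard error of alpha_1.** Generalised least squares, with and without X_i*t, 30% dropout equal in all groups:

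| Divergence by mandate at week 26 | SE too large by |
|---|---|
| 0 points | 0% |
| 10 points | about 2 to 2.5% |
| 15 points | about 4 to 6% |
| 20 points | about 7 to 10% |

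Two simulated cases with a 10-point divergence, p = 0.5 and 10 sites:

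- No random slope: SE 0.1003 as written, 0.0979 with the term; 0.1003/0.0979 = 1.025.
- Random-slope SD 0.5: SE 0.1155 as written, 0.1135 with the term; 0.1155/0.1135 = 1.018.

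**Step 3: power.** For a treatment effect of 0.385 points per week, power is about Phi(0.385/SE - 1.96):

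- No random slope: Phi(1.88) = 0.970 as written, Phi(1.97) = 0.976 with the term.
- Random-slope SD 0.5: Phi(1.37) = 0.915 as written, Phi(1.43) = 0.924 with the term.

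The loss is at most about 1 percentage point. These powers serve only to compare the two models; they do not check the plan's 80%.

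**Step 4: validity.** Under the null, the model as written rejected in 3.2 to 5.8% of replicates across scenarios (1,000 to 2,000 replicates each), close to 5%. Mean alpha_1 was about zero when dropout was equal or depended on mandate only.

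**Step 5: joint dropout (hypothetical).** Suppose 50% of mandated TAU participants and 10% of mandated STAGE-12 participants drop out, with 30% of voluntary participants in each arm. With a 10-point divergence and p = 0.5, the null estimate is off by 0.0385 per week (0.0385 * 26 = 1.0 point at week 26), against about zero with X_i*t in the model. Rejection was 5.4%. A milder pattern (final dropout 50% TAU voluntary, 30% STAGE-12 voluntary, 20% mandated in both arms) gives an error of 0.5 to 0.6 points at week 26 for a 10-point divergence and 1.1 to 1.2 points for a 20-point one. The term removes it.

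**The case against.** The strongest reply is that a stratification factor entered as a main effect is ordinary practice, a stratum-by-time term is optional, and the printed model gives a valid test. This stands, and it limits the point to efficiency.

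A reader might infer that court mandate is ignored in the primary test. The equations do not support that. X_i*phi is in the model and, because there is no treatment main effect, alpha_1 also draws on post-baseline level differences. Dropping X_i*phi would raise the SE of alpha_1 by about 1% for a 10-point level difference and 3 to 4% for 20 points, so the level adjustment does reach the test slightly.

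A reader might also infer that alpha_1 is biased or the test invalid. That does not follow either. Bias needs a slope difference by mandate and dropout that differs by mandate and arm jointly, and nothing in the protocol says that either will occur. Section 10.5 already discusses data that are not missing completely at random, names pattern-mixture models and singles out the effect of arm on missingness.

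Finally, the larger SE figures need mandate groups to diverge by 15 to 20 points, which is 1.5 to 2 times the 10-point difference that section 10.6 treats as clinically meaningful. That is fair; the 10-point row is the one to weigh. What remains is that two strata are handled differently without a stated reason, and aligning them costs almost nothing.

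**Conclusion.** The point holds as a minor, free improvement in efficiency. Court mandate is adjusted for in level and not in slope, while site is adjusted for in both, and the treatment effect is tested in the slope. For a 10-point divergence between mandate groups at week 26, the SE of alpha_1 is about 2 to 2.5% too large and at most about 1 point of power is lost. With no divergence the loss is nil; it grows only if the divergence is larger. The loss is conservative: it does not produce false positives. The bias result is conditional on an assumed joint dropout pattern and should not be read as a prediction for this trial. Mandate prevalence, mandate-specific slopes and mandate-specific dropout are all assumptions here.

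**What to change.** In section 10.3.1, write the slope equation as

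beta_ij = alpha_0j + alpha_1*I(STAGE-12) + alpha_2*X_i + b_ij,

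keeping X_i*phi in Level 1. Make the same change in the secondary hierarchical models with two or more post-baseline visits: non-stimulant use, ASI composite scores, 12-step meeting attendance and 12-step activities.

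Do not extend it to spirituality (10.4.2.1.3) or perceived barriers (10.4.2.1.4). These are measured at baseline and week 8 only. With a single post-baseline visit, X_i*t is 8*X_i at the nominal time, so it cannot be separated from X_i*phi.

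The cost is one fixed-effect parameter per model and a change of wording in the protocol and any statistical analysis plan; no data are added. It should be made before unblinded outcomes are seen, so that the term is not open to the charge of being data-driven. If the sponsor prefers the model as printed, a sentence saying why the two strata are handled differently would suffice.

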10.4.2.1.3 Hypothesis

STAGE-12 will result in a greater increase on measures of spirituality than TAU.

The outcome variable will be a measure of spirituality as assessed by the Spiritual Involvement and Beliefs Scale at baseline and week 8/end of treatment. The data will be analyzed using a hierarchical linear model similar to the model for the primary outcome. Let α_{SP} denote the effect of the STAGE-12 treatment in the Level-2 model. The hypotheses H₀: α_{SP} =0 vs. H₁: α_{SP} ≠0 will be evaluated and rejection of the null hypothesis with α_{SP} > 0 would indicate that STAGE-12 treatment results a greater increase on measures of spirituality than TAU.

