10.4.2.1.4 Hypothesis

STAGE-12 will result in a greater reduction in 12-step perceived barriers to 12-step involvement than TAU.

The outcome variable will be a measure of perceived barriers to 12-step involvement as assessed by the Perceived Barriers subscale of the Survey of Readiness at baseline and week 8/end of treatment. The data will be analyzed using a hierarchical linear model similar to the model for the primary outcome. Let α_{PBAR} denote the effect of the STAGE-12 treatment in the Level-2 model. The hypotheses H₀: α_{PBAR} =0 vs. H₁: $\alpha_{PBAR} \neq 0$ will be evaluated and rejection of the null hypothesis with

 α_{PBAR} < 0 would indicate that STAGE-12 treatment results a greater reduction on measures of 12-step ambivalence than TAU.

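### The primary model in 10.3.1 leaves the observed baseline stimulant use out, although 10.6 says it enters as a covariate; using it would gain modest precision at no cost

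*Protocol*

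**What the plan says.** Protocol 10.3.1 says that percent of days of stimulant use is "assessed at baseline, weeks 4 and 8/end of treatment, 3 months and 6 months", so a baseline value exists for the primary outcome. The model in that section is then built as follows.

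- The responses run over k = 1 to n_i, where n_i "is the number of post-baseline assessments for participant" i. Baseline is not among them.
- The one covariate, X_i, "is a baseline variable describing whether participant i was court mandated for treatment".
- The symbol β_0ij "is the baseline percent of stimulant use", yet a Level-2 equation follows under the words "The Level-2 model also describes the baseline outcome measure for participant" i. It sets β_0ij to a site intercept plus a normal subject-level error.
- Treatment enters only through the slope, and the test is of α_1 = 0.

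Protocol 10.6 lists measurements at weeks 4, 8, 13 and 26 and adds that "the baseline value is to be entered as a covariate".

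Sections 10.4.2.1.3 and 10.4.2.1.4 call for a model similar to the primary one for two scales with a single follow-up. Spirituality is to be analysed "as assessed by the Spiritual Involvement and Beliefs Scale at baseline and week 8/end of treatment". Perceived barriers come from the "Perceived Barriers subscale of the Survey of Readiness at baseline and week 8/end of treatment".

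**The concern.** A quantity that is given a mean and a random error is a latent intercept, estimated from the follow-up data. It is not the measured pre-treatment value. So the model in 10.3.1 does not contain the covariate that 10.6 announces, and two analysts could fit different primary models from the same protocol.

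At stake is efficiency. Past stimulant use can be expected to correlate with later use. Leaving it out widens the interval for α_1 and leaves any chance difference between arms at baseline unadjusted. A smaller question arises for the two scales above: one post-baseline value per person cannot support a model with a random intercept, a random slope and a residual.

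**Working it through.** **The plan's own figures.** The effect size reproduces: 21.3/90 = 23.7% and 10/23.7 = 0.42. The sample-size table in 10.6 (30% attrition: 139, 165 and 191 per arm at rho 0.3, 0.5 and 0.7) does not reproduce from the four stated visits. With a difference growing linearly to 0.4 SD and weights proportional to time, those visits give 147, 180 and 212. Visits at weeks 8, 13 and 26 alone give 138, 163 and 189. In both the document and this check, n rises with rho. If a baseline with the same rho were adjusted for, the three-visit version would give 117, 106 and 78, falling with rho. The table therefore shows no baseline adjustment, unless its SD and rho are meant as conditional on baseline, which is not said.

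**Precision of α_1 in the 10.3.1 model.** Inputs from 10.6: weeks 4, 8, 13, 26; compound symmetry; rho 0.5 (0.3 to 0.7 tabulated); 70% retention with even dropout; SD 23.7; 200 per arm; two-sided 0.05; 80% power. One input is an assumption: that the correlation of baseline with each follow-up equals rho. The random slope is set to zero at first.

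For a participant seen at the first m visits, in units of outcome variance, the information is:

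- without baseline: I_m = [Σt² − ρ(Σt)²/(1 + (m−1)ρ)] / (1−ρ)
- with baseline: I_m = [Σt² − ρ(Σt)²/(1 + mρ)] / (1−ρ)

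The second formula is the same whether baseline is a covariate or a week-0 response with a common arm mean. For all four visits Σt² = 16 + 64 + 169 + 676 = 925 and (Σt)² = 51² = 2601. At rho 0.5:

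| Last visit seen | Share of arm | Without baseline | With baseline |
|---|---|---|---|
| none | 0.075 | 0 | 0 |
| week 4 | 0.075 | 2(16 − 16/2) = 16 | 2(16 − 16/3) = 21.3 |
| week 8 | 0.075 | 2(80 − 144/3) = 64 | 2(80 − 144/4) = 88 |
| week 13 | 0.075 | 2(249 − 625/4) = 185.5 | 2(249 − 625/5) = 248 |
| week 26 | 0.70 | 2(925 − 2601/5) = 809.6 | 2(925 − 2601/6) = 983.0 |

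Average information per randomised participant:

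- without baseline: 0.075 × 265.5 + 0.70 × 809.6 = 586.6
- with baseline: 0.075 × 357.3 + 0.70 × 983.0 = 714.9

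The variance ratio is 586.6/714.9 = 0.82. The same calculation gives 0.90 at rho 0.3 and 0.75 at rho 0.7.

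**Detectable difference at week 26**, from 2.80 × 26 × 23.7 × √(2/(200 × I)):

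- without baseline: I = 586.6 gives 7.1 points
- with baseline: I = 714.9 gives 6.5 points

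Equivalently, the model without baseline needs 200 × 714.9/586.6 ≈ 244 per arm to match 200 per arm with it.

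**Random slope added.** The model in 10.3.1 has one, and the protocol gives no size for it. With an assumed slope SD of 0.6 or 1.0 outcome SD at week 26, the variance ratio at rho 0.5 becomes 0.87 or 0.91.

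**The two week-8 scales.** With one value per person at t = 8, the data identify only the total σ_0² + 64σ_b² + σ², so the three components cannot be separated. The arm difference in means is still identified, and α_1 is that difference divided by 8.

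**The case against.** The best defence is that 10.3.1 means baseline to be a response at week 0. It names baseline among the assessment times, labels the intercept as baseline use, and puts no treatment term in the intercept. Under that reading precision equals the covariate version and nothing is lost. However, the section indexes the responses explicitly over post-baseline assessments, which contradicts it, and 10.6 would still need changing. What stands is that the text can be read more than one way, so the loss applies to the model as written and not necessarily to the one intended.

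It is also fair that the size of the gain is uncertain. The protocol says it has no information on the correlation pattern, its rho is stated alongside the four follow-up measurements, and variable slopes shrink the gain.

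A reader might infer more than this, and the documents do not support it:

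- *A 40% gain.* At rho 0.5 the variance of the mean of the four follow-up values falls from 0.625 to 0.375 of the outcome variance. The primary test is of a slope difference, so that figure does not apply.
- *A biased comparison or a trial sized on an adjustment it does not make.* Randomisation protects validity either way, and the sample-size table does not visibly use baseline adjustment.
- *Reading the intercept as the observed value leaves imbalance uncorrected.* Its coefficient would then be fixed at 1. A change score does subtract the imbalance, and over-corrects when the true coefficient is below 1. That still differs from the covariate in 10.6.
- *The spirituality and perceived-barriers analyses cannot be fitted.* Only the stated variance structure fails. Both endpoints lie outside the key secondary list in 10.4 and are exploratory.

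**Conclusion.** The contradiction between 10.3.1 and 10.6 is real, and as written the collected baseline stimulant use is not used in the primary analysis. The consequence is lost precision and unadjusted chance imbalance. With baseline included, the variance of the α_1 estimate falls by about 10%, 18% and 25% at rho 0.3, 0.5 and 0.7. These figures assume that the baseline-to-follow-up correlation equals rho, compound symmetry, 30% even dropout and no slope variation. At rho 0.5 the fall is about 13% or 9% for an assumed random-slope SD of 0.6 or 1.0 at week 26. The gain also depends on treatment entering only through the slope with a common intercept, as 10.3.1 specifies. With a separate intercept for each arm, the covariate would change the slope variance by 0 to 3%. For the two week-8 scales the variance components are not identifiable, but the arm difference is.

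**What to change.** In 10.3.1, add the observed baseline percent of stimulant days to model (1) as a fixed covariate with an estimated coefficient, keeping site and court mandate. Describe β_0ij as a random intercept, not as baseline use. Do the same for the other hierarchical-model endpoints, each with its own baseline. An acceptable alternative is to index the responses from k = 0 with a common arm mean at baseline and to change 10.6 to match. In either case, state in 10.6 whether the SD and rho used for sizing are before or after baseline adjustment.

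For the Spiritual Involvement and Beliefs Scale and the Perceived Barriers subscale, replace the slope model with an ANCOVA of the week-8 score on the baseline score.

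The cost is wording only, since all these baseline measures are already scheduled.
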